### 10.3. Evaluation during treatment

**Counting Cycle Duration:** During induction and consolidation, one cycle is defined by start of chemotherapy and will continue until the start of next chemotherapy (i.e. induction 1 = cycle 1 and may exceed 28 days). During maintenance, cycles will be 28 days in maximum duration (28 days = 1 cycle).

It is assumed subjects will be in the hospital for chemotherapy (induction and consolidation). Required study patient evaluations should be performed as an inpatient or outpatient including:

1. Physical examination (with ECOG PS, vital signs and weight) and medical history update (including concomitant medications), and documentation of adverse events:
  - a. During induction(s): Routinely per institutional standard of care , at response assessment visit (Day 14-28), and at count recovery (or day 42) whichever occurs first.
  - b. During consolidation(s) Day 1 of crenolanib and then routinely per institutional standard of care
  - c. During maintenance: Day 1 and then per site standard schedule but no less frequent than every 2 months ( $\pm$ 1 month).
2. EKG measurements to be obtained during induction and consolidation therapy.
  - a. EKG to be obtained 2 hour ( $\pm$  30 minutes) post first dose of crenolanib in consolidation 1.
3. CBC with platelet count and differential (differential may be omitted if WBC is  $<0.5 \times 10^9/L$ ) must be obtained at least
  - a. During induction(s): Routinely per institutional standard of care (at least once weekly), at response assessment visit (Day 14-28), and at count recovery (or day 42) whichever occurs first.
  - b. During consolidation(s): Routinely per institutional standard of care (at least once weekly).
  - c. During maintenance: Day 1 of each cycle
4. Chemistry panel including creatinine, total bilirubin, ALT and AST must be obtained at least
  - a. During induction(s): Routinely per institutional standard of care (at least once weekly), at response assessment visit (Day 14-28), and at count recovery (or day 42) whichever occurs first.
  - b. During consolidation(s): Routinely per institutional standard of care (at least once weekly).
  - c. During maintenance: Day 1 of each cycle
5. Bone marrow aspirations will be taken as follows:
  - a. During induction (s): Between days 14-28, bone marrow is obtained per standard of care to evaluate for remission/response to therapy and at time of count recovery or Day 42 (whichever occurs first)
  - b. Bone marrow sampling during consolidations should occur per institutional standard of care.

- c. During maintenance: should occur per institutional standard of care (reference study calendar appendix IV).
6. Blood and marrow samples for translational research including pharmacokinetic analysis will be obtained as defined in Section 11 and lab manual. Every effort should be made to collect correlative studies at all time points for all patients; however, missing collection in one or more of these time points will not be considered a protocol deviation/violation.
7. Serum or urine pregnancy test for women of child bearing capacity should be done every six months while on study.

#### **10.4. At time of progression or completion of study**

1. Medical history and physical exam (includes documentation of current medications)
2. Weight, vital signs, ECOG Performance Status (Appendix II)
3. Adverse event documentation
4. CBC with platelet count, differential (differential may be omitted if WBC is  $<0.5 \times 10^9/L$ )
5. Chemistry panel including creatinine, total bilirubin, ALT, and AST
6. bone marrow and whole blood samples
7. Evaluation of FLT3-D835, FLT3-ITD and other mutational status when available

\* Every effort should be made to collect optional procedures at all time points for all patients; however, missing collection in one or more of these time points will not be considered a protocol deviation/violation.

Procedures that are to be performed at the planned subject visits will be granted an exemption if the subject is hospitalized and unstable, or otherwise medically unstable as determined by investigator and unable to travel to the study sites. In the latter case, the investigator is responsible to ensure that the planned protocol procedures are performed at a local hospital and provide oversight. Appropriate documentation and source documents shall be obtained and information recorded onto study CRFs.

## 11. PHARMACOKINETIC AND CORRELATIVE STUDIES

The participating institution will receive a laboratory kit containing blood collection tubes, labels, and a lab manual with collection instructions from AROG for the collection, processing and shipping of samples from consenting subjects. Site should contact AROG (Appendix VIII) to request lab kits in anticipation of each patient enrolled on the study.

Correlative samples to be collected include but are not limited to:

1. Serum for pharmacokinetic (PK) analysis (selected sites only)
2. Bone marrow aspirate (BMA) samples
3. Bone marrow smears
4. Whole blood sample

### **Sampling Schedule for PK (selected sites only)**

Serial blood samples for PK will be drawn for correlative research. See lab manual for forms. During crenolanib treatment, PK will be drawn for the following time points:

#### **Day 1 of crenolanib administration following Induction 1**

- a. pre-dose
- b. post-dose 2 hours ( $\pm$  15 minutes)
- c. post-dose 4 hours ( $\pm$  30 minutes)
- d. post-dose 8 hours ( $\pm$  2 h)
- e. post-dose 24 hours ( $\pm$  6 h) prior to first dose of the day

#### **Day 15 of crenolanib administration following Induction 1**

- a. pre-dose
- b. post-dose 4 hours ( $\pm$ 30 minutes)

For patients who proceed to consolidation with HiDAC:

#### **Day 1 of crenolanib administration following Consolidation 1**

- a. pre dose
- b. post-dose 4 hours ( $\pm$ 30 minutes)
- c. post-dose 8 hours ( $\pm$  2 h)

**Please make sure that the time and dose of last four crenolanib administrations are captured on PK forms.**

### **Sampling Schedule for Bone Marrow Aspirates**

At the time of each routine marrow sampling, an additional aspiration of 2.5 mL should be drawn for research purposes and placed in a heparinized cell preparation tube. See lab manual for required form.

Scheduled bone marrow time points per protocol:

- a. During induction(s): day 14-28 and at time of count recovery (or Day 42), whichever occurs first
- b. During consolidations: as per the institutional standard of care

- c. Maintenance: as per the institutional standard of care.
- d. When patient is determined to have progressive disease by the treating physician (loss of CR/CRi).

**Sampling Schedule for Whole Blood Collection**

Samples of 5-10 mL of whole blood are drawn and placed in heparinized cell preparation tubes for other correlative science research studies. See lab manual for required form. Samples should be drawn at the following two time points:

- a. Pre-administration of first dose of anthracycline in induction 1 (when applicable),
- b. Upon progression

**Sample Processing Instructions**

See lab manual for processing, storage and shipment of samples.

**Sampling Schedule for Other Correlative Studies**

Additional samples for correlative research may be collected at any time while the patient is on study, at the discretion of the investigator or as requested by the sponsor. These may include assays for resistance studies for cases in which responses are noted but not durable. Samples can be stored and collected and send at interim intervals. AROG may request the investigator obtain additional samples from the patients; the total blood drawn for these studies will be less than 200 ml in any month.

Samples will be stored at AROG or its designated facility for future correlative science research studies.

## 12. RESPONSE DEFINITIONS

### 12.1. Response Criteria

Response criteria will be adapted from the International Working Group for AML. [9] Responders are newly diagnosed patients receiving study drug who obtain a CR, CRi, or PR, with or without cytogenetic response, hematologic improvements, and morphologic leukemia-free state. Briefly, criteria are as follows:

1. Complete remission (CR):
  - a. Peripheral blood counts:
    - i. No circulating blasts
    - ii. Neutrophil count  $\geq 1.0 \times 10^9/L$
    - iii. Platelet count  $\geq 100 \times 10^9/L$
  - b. Bone marrow aspirate and biopsy:
    - i.  $< 5\%$  blasts
    - ii. No Auer rods
    - iii. No extramedullary leukemia
2. Complete remission with incomplete blood count recovery (CRi):
  - a. Peripheral blood counts:
    - i. No circulating blasts
    - ii. Neutrophil count  $< 1.0 \times 10^9/L$ , or
    - iii. Platelet count  $< 100 \times 10^9/L$
  - b. Bone marrow aspirate and biopsy:
    - i.  $< 5\%$  blasts
    - ii. No Auer rods
    - iii. No extramedullary leukemia
3. Partial remission:
  - a. All CR criteria except:
  - b.  $\geq 50\%$  reduction in bone marrow blast but within 5-25% or
  - c. Marrow blasts  $< 5\%$  with persistent Auer rods
4. Morphologic leukemia-free state:
  - a. Bone marrow:  $< 5\%$  myeloblasts
5. Hematologic Improvement (HI):  
Hematologic response must be described by the number of positively affected cell lines.
  - a. Blast response (B)
    - i. At least a 50% reduction in blast percentage in peripheral blood (if  $> 5\%$ ) or bone marrow

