**Table 3 Cohort B: Cytarabine, idarubicin induction**

Drug	Dose	Mode	Days
Cytarabine	100 - 200 mg/m  /day	IV continuous infusion over 24 hrs	Days 1-7
Idarubicin	12 mg/m 	intravenously daily over 10-15 mins	Days 1-3

If after induction 1, the bone marrow is hypoplastic (<10 % cellularity) on day 14-28 and contains less than 5 percent blast cells, further chemotherapy treatment can be deferred and the marrow examination repeated weekly until marrow recovery, or per the discretion of the treating physician. A repeat bone marrow should be performed at time of hematological remission or Day 42, whichever occurs first. Crenolanib treatment may be continued during this period as per the discretion of the treating physician.

If after induction 1, the bone marrow shows residual disease without a hypocellular marrow, a second course of the same induction remission therapy (or lower dose of anthracycline per Tables 2 and 3) can be given at the decision of the treating physician. Timing and/or necessity of bone marrow evaluation following second induction will follow the same schedule as induction 1. Crenolanib must be held for 72 hours prior to the start of the next chemotherapy.

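### CRi in Section 12.1 has no marrow cellularity or recovery condition, so a hypoplastic Day 14-28 marrow can be counted as a primary response

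*Combined protocol and SAP*

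**What the plan says.** Section 12.1 gives the responder rule: "Responders are newly diagnosed patients receiving study drug who obtain a CR, CRi, or PR", and adds "with or without cytogenetic response, hematologic improvements, and morphologic leukemia-free state". CRi requires no circulating blasts, neutrophils below 1.0 or platelets below 100 x10^9/L, marrow blasts under 5%, no Auer rods and no extramedullary leukemia. Item 4, "morphologic leukemia-free state", requires only marrow myeloblasts under 5% and is not among the three responses that make a responder.

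Section 8.2.1 (text below Table 3) anticipates an empty marrow: "If after induction 1, the bone marrow is hypoplastic (<10 % cellularity) on day 14-28 and contains less than 5 percent blast cells". In that case further chemotherapy may be deferred and the "marrow examination repeated weekly until marrow recovery, or per the discretion of the treating physician". A further marrow is due at hematological remission or Day 42, whichever is earlier. For a second course, "bone marrow evaluation following second induction will follow the same schedule as induction 1".

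Section 10.3, item 5a, says that between Days 14 and 28 "bone marrow is obtained per standard of care to evaluate for remission/response to therapy and at time of count recovery or Day 42". Appendix IV labels the Day 14-28 visit as the response assessment.

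Section 13.3.2 makes overall response rate the primary end-point of the expansion phase and requires one dose of study drug and one marrow assessment. It does not say which marrow counts. Section 13.7 only points back to 12.1.

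**The concern.** The Day 14-28 marrow is taken to judge response, and the protocol itself expects that some of these marrows will be almost empty. Section 8.2.1 handles such a marrow as awaiting recovery, but the CRi criteria contain nothing that holds it back from being scored as a response. A low blast percentage in a marrow with under 10% cellularity shows that the marrow has been cleared. It does not show that normal marrow has returned without leukemia.

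CRi is one component of a primary response rate in a non-randomized trial, which Section 13.1.2 sets beside external rates of 66-69% and 74-76%. No concurrent control arm would carry the same classification error. Patients who die or are lost in aplasia could enter the numerator. So could patients whose leukemia regrows later, if best response is used; the plan does not say whether it is.

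**Working it through.** **1. The plan's own precision figure.** Section 13.1.2 gives about 120 patients and a 95% interval of ±5% at a 90% rate. The Wald half-width is 1.96 × √(0.90 × 0.10 / 120) = 5.37 points, which agrees with the stated figure after rounding. It serves only as a yardstick below.

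**2. The criteria applied to a test case.** Take neutrophils 0.1 and platelets 20 x10^9/L, no circulating blasts, marrow blasts 2%, cellularity 5%, no Auer rods and no extramedullary leukemia, in a patient who has received study drug.

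| Class in 12.1 | Result | Reason |
|---|---|---|
| CR | Not met | Neutrophils and platelets both below the CR limits |
| CRi | Met | Each written condition is satisfied; cellularity is not among them |
| Morphologic leukemia-free state | Met | Blasts under 5% |
| Responder | Yes | Through CRi |

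The count limits for CR and CRi are complementary: either both counts reach the CR limits or at least one does not. So any patient on study drug with marrow blasts under 5% and none of the three excluding signs is either CR or CRi, however empty the marrow.

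**3. Whether another section prevents this.**
- Section 8.2.1 leads to a later marrow but does not make that marrow the one that decides response.
- Section 10.3 and Appendix IV treat Day 14-28 as a response assessment.
- Section 13.3.2 is satisfied by a single marrow.
- Section 13.7 adds nothing to 12.1.
- Count recovery is defined in Appendix IV, but only to time the later visit.

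A patient who dies after a hypoplastic Day 14-28 marrow, and before the repeat, therefore remains a CRi.

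**4. Size per patient.** Such patients already have a marrow, so the denominator is unchanged and only the numerator moves.
- N = 120: 1/120 = 0.83 points.
- N = 72 (expansion phase only): 1/72 = 1.39 points.

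**5. Illustration.** The documents do not give the number of such patients. For an assumed 1 to 5:
- N = 120: 1/120 to 5/120 = 0.83 to 4.17 points.
- N = 72: 1/72 to 5/72 = 1.39 to 6.94 points.

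Starting from 108/120 = 90%, removing 3 such patients gives 105/120 = 87.5%, and removing 6 gives 102/120 = 85.0%. It would take 6 to 7 patients (5.37/0.83 ≈ 6.4) to shift the rate by the half-width in step 1.

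**The case against.** The strongest reply is that 12.1 is an abbreviated statement of criteria adapted from a cited source, and that Section 13.1 leaves analysis detail to a separate SAP. Either could contain the missing condition. That stands as a limit: the finding concerns the text supplied. But 12.1 is the only definition that the statistics section uses, and followed literally it gives the result above.

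The second reply is that 8.2.1 largely deals with the case, because surviving patients should have a repeat marrow by Day 42. This also stands, and it narrows the exposed group mainly to those who die or are lost before the repeat marrow. It does not close the gap, because the repeat marrow is not named as decisive.

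Three stronger readings are tempting, and the documents do not support them.
- A reader might take the overlap with "morphologic leukemia-free state" as the error. Every CR and every CRi meets item 4, the responder sentence allows for that, and CRi adds three further conditions.
- A reader might infer that patients with poor counts are wrongly called CRi. Incomplete count recovery is what CRi means. With a non-hypoplastic marrow, those patients are properly CRi, including before Day 42.
- A reader might infer that the response rate will be materially inflated. Nothing supplied gives the frequency. At N = 120 even the assumed five patients (4.17 points) stay inside the 5.37-point half-width, and the descriptive analysis has no stated test or threshold that could be crossed.

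It is also fair that the 10% figure serves in 8.2.1 to decide on deferring chemotherapy. Using it to classify response is a choice, made because it is the protocol's own figure for a hypoplastic marrow.

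**Conclusion.** The concern holds in a limited form. As written, a hypoplastic marrow at Day 14-28, after either induction, establishes CRi and a primary response in a cytopenic patient on study drug with no circulating blasts, Auer rods or extramedullary leukemia. Relative to a rule that asks for a non-hypoplastic marrow, the error can only raise the rate, by 0.83 points per patient at N = 120 or 1.39 at N = 72. The total is unknown, and 1 to 5 patients is an assumption.

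The conclusion rests on three conditions: no limiting rule exists in the cited criteria or the separate SAP, neither of which was available; the one-marrow requirement in 13.3.2 governs the overall response rate, although that sentence names the complete response rate; and, for patients with later regrowth only, best response is the rule in use. The point should be settled before the response analysis, because it affects who counts in a primary end-point and wording can resolve it.

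**What to change.** For the response-rate analysis only:

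1. In 12.1 and 13.3.2, state that a marrow with under 10% cellularity does not by itself establish CRi. Response is then taken from a later marrow with cellularity of at least 10%, after either induction. A marrow at or above that level that meets the CRi conditions may establish CRi at any scheduled assessment.
2. State that a patient with no such later marrow, including because of death, stays in the denominator as a non-responder.
3. Report how many patients would have been CRi on a hypoplastic marrow alone, and give the response rate with them counted as a sensitivity figure.
4. State that this classification is for analysis and does not alter treatment, maintenance or discontinuation decisions elsewhere in the protocol (Sections 7.4.1, 8.2.1 and 8.2.3).

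Cost: wording in two sections, one count and one extra rate in the report. Cellularity must be recorded for the Day 14-28 marrow. Appendix IV already schedules a biopsy there, although Section 10.3 speaks of aspirations taken under standard of care, so sites should be told that the value is needed. No marrow is added. The reported rate may be slightly lower, and a few true responders without a later marrow will count as non-responders; item 3 shows the largest number this could be.

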## 13. STATISTICAL CONSIDERATIONS

### 13.1. Statistical and analytical plans

The statistical analysis of this study will be the responsibility of AROG Pharmaceuticals or its designees. The clinical research physician/scientist and statistician will jointly be responsible for the appropriate conduct of an internal review process for the final study report and any study-related material to be authorized for publication by AROG or its designees. A statistical analysis plan (SAP) will be prepared as a separate document that details the planned analyses and presentation of the study results.

#### 13.1.1. General considerations

The statistical analyses will be performed by cohort and in some cases, with the cohorts combined. Descriptive statistics will be used to summarize the safety and efficacy data for this study. Continuous data will be summarized by the number of patients, mean, standard deviation, median, minimum, and maximum value. Categorical data will be summarized by the number and percentage of patients in each category. Time-to- event endpoints will be summarized using the cumulative incidence and Kaplan-Meier methodology, as appropriate.

#### 13.1.2. Determination of sample size

A total of approximately 120 patients will be enrolled. The study consists of a safety phase and an expansion phase. The safety phase has two arms in which patients will receive cytarabine in combination with daunorubicin (Cohort A) or with idarubicin (Cohort B) during standard 7+3 therapy with Crenolanib. The safety of each arm will be evaluated separately and once the safety is established, an expansion phase will be opened in which patients can receive either chemotherapy regimens.

During the initial safety phase, the two cohorts, each consisting of approximately 24 patients, will be analyzed separately and initially enroll 12 patients to receive crenolanib with 1-2 courses of standard induction chemotherapy. If the early safety stopping criteria are not met for a cohort, then 12 additional patients may be enrolled in that cohort in order to further characterize the safety and tolerability of the combination.

Once the safety of the combinations is determined, a single arm expansion phase will be initiated to further confirm the safety and assess the clinical benefit of the combination of standard induction chemotherapy with crenolanib.

Historically, patients with newly diagnosed FLT3+ve AML achieve a 66% - 69% response rate with induction chemotherapy only. (Mandelli et al. J Clin Oncol. 2009;27(32):5397-403) In recent years, Midostaurin (a FLT3 TKI) has shown an improvement of response rate to 74-76% with the combination of Midostaurin to standard induction chemotherapy. (Schlenk et al. Blood 2016; 128(22): 449) This study will enroll approximately 120 patients with the following confidence intervals based on projected response rate. A response rate of 90% will have a 95% CI of  $\pm 5\%$ . That is to say that if we treat 120 patients and observe a 90% response rate, we are 95% sure that the true response rate is between 85% to 95%.

**13.2. Safety monitoring during the initial safety phase**

Adverse events, as defined in Section 14.1, will be monitored during the treatment and post-treatment follow up periods. Adverse events will be monitored on a continuous basis by the sponsor.

The Protocol Safety Committee will review safety data from this trial on a periodic basis. The committee also will monitor the safety outcomes listed below for purposes of determining if enrollment in one or both cohorts should continue or be halted. Within each cohort, up to 6 patients will be initially enrolled. For the first 6 patients, patients will be enrolled in a sequential manner such that no more than 3 patients are within 30 days of starting induction 1 therapy. Enrollment will be halted within a cohort if an apparent increase is observed in the occurrence of one or more of the following outcomes:

- Early mortality due to any cause
- Expected, non-hematologic, crenolanib-related toxicity (CTCAE Grade 4)
- Unexpected, non-hematologic, crenolanib-related toxicity (CTCAE Grade 4)

The criteria used to determine if enrollment will be halted are described in sections 13.2.1, 13.2.2 and 13.3.3.

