**Safety analysis:**

During the initial safety phase, twelve patients will be enrolled onto each cohort and if the early stopping rule criterion are not met than approximately 12 additional patients will be enrolled onto each cohort. Safety monitoring will be performed separately for each cohort and enrollment will be halted within a cohort if stopping rules are met for early mortality due to any cause, increase in expected non-hematologic crenolanib-related grade 4 adverse events, or any unexpected non-hematologic crenolanib-related grade 4 adverse events.

Stopping rules during the initial safety phase are the following: If the observed mortality rate exceeds 10 % and 20% at day 30 and 60, respectively, enrollment will be halted pending Protocol Safety Committee review. If an observed increase of expected non-hematologic crenolanib-related grade 4 adverse events exceeds 20% during the first 60 days of treatment further enrollment will be halted pending Protocol Safety Committee review. If an observed increase of unexpected non-hematologic crenolanib-related grade 4 adverse event exceeds 15% during the first 60 days of treatment further enrollment will be halted pending Protocol Safety Committee review.

During the expansion phase, safety monitoring will be performed for the entire per protocol patient population (defined as those who receive at least one dose of study drug) and in a separate analysis dictated by chemotherapy agent used.

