**13.2.1. Excessive early mortality**

Early stopping rules for excessive mortality will be applied in the safety phase of the study. Early mortality is defined for this study as death due to any cause within 30 and 60 days of the initiation of study treatment. In the VALOR trial, all-cause mortality rates of 7.9% and 19.7% were reported, respectively, for patients with relapsed/refractory AML who received cytarabine and placebo as induction therapy. [14] The 30-day mortality rate of 7.9% from the VALOR trial is similar to the 28-day mortality rate of 10.3% that was reported from a retrospective analysis of more than 3000 patients with newly diagnosed AML, the majority of whom were treated with cytarabine-based regimens as induction therapy.[11]

Based on the above considerations, enrollment in a cohort will be halted if the observed 30- and 60-day early mortality rate exceeds 10% and 20%, respectively, as follows: if 1 or more of the first 6 patients enrolled within a cohort die prior to Day 30 then enrollment of additional patients within that cohort will be halted pending review by the Protocol Safety Committee. Additionally, enrollment will be halted within a cohort if 2 or more of the patients die prior to Day 60. Otherwise, 6 additional patients will be enrolled within the cohort provided none of the other stopping criteria have been met.

For the second group of 6 patients within a cohort, if 2 or more of the patients enrolled within a cohort die prior to Day 30, then enrollment of additional patients will be halted pending review by the Protocol Safety Committee. Similarly, if 3 or more of the patients enrolled within a cohort die

prior to Day 60, then enrollment of additional patients will be halted for that cohort. If these and the other early stopping criteria are not met, then the 12 additional patients will be enrolled within the cohort.

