### **13.2.2. Excessive expected crenolanib-related toxicity**

Early stopping rules for excessive expected crenolanib-related toxicity will be applied in the safety phase of the study. In clinical studies of crenolanib as single-agent therapy, the following treatment-related, non-hematologic, adverse events were the most frequently reported, irrespective of severity:

- hepatic dysfunction
- nausea, vomiting, and diarrhea
- ascites, edema, and effusions

The majority of these events were CTCAE severity grade 1-3, with grade 4 representing less than 5% of total cases reported. It's anticipated that these or similar adverse events also occur with relatively higher frequency for AML induction regimens that include cytarabine, idarubicin, or daunorubicin. Nonetheless, for purposes of monitoring enrollment in this study, the adverse events listed above represent the expected non-hematologic crenolanib-related toxicities. If the observed rate of expected, non-hematologic, crenolanib-related toxicity with CTCAE severity grade 4 exceeds 20% during the first 60 days of treatment, then enrollment will be halted as follows:

If 2 or more of the first 6 patients enrolled within a cohort experience a CTCAE grade 4, non-hematologic, expected crenolanib-related adverse event prior to Day 60 then enrollment of additional patients within that cohort will be halted pending review by the Protocol Safety Committee. Otherwise, 6 additional patients will be enrolled within the cohort provided none of the other stopping criteria have been met. Upon enrollment of the 6 additional patients within a cohort, if 3 or more of the patients enrolled within a cohort experience such an event prior to Day 60, then enrollment of additional patients will be halted pending review by the Protocol Safety Committee. If these and the other early stopping criteria are not met, then 12 additional patients will be enrolled to the cohort.

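### The safety phase has two conflicting first steps (6 or 12 patients per cohort), and no section says whether patients 7 and 13 wait for the Day-60 counts that the halting rules use

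*Combined protocol and SAP*

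**What the plan says.** Section 13.2 starts small: "Within each cohort, up to 6 patients will be initially enrolled". It then spaces that first group, counting from the start of induction 1: "For the first 6 patients, patients will be enrolled in a sequential manner such that no more than 3 patients are within 30 days". No spacing is given for later patients.

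Sections 13.2.1 to 13.2.3 set halting counts for the first 6 patients and again after 6 more. If no count is reached, 12 further patients follow, which makes 24 per cohort. There are four rules: death by Day 30, death by Day 60, expected grade 4 toxicity and unexpected grade 4 toxicity. The last three run to Day 60. The expected-toxicity rule, for example, counts patients who "experience a CTCAE grade 4, non-hematologic, expected crenolanib-related adverse event prior to Day 60". Each subsection makes the next group conditional on the criteria not having been met.

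The other two accounts of the same phase differ. The synopsis, under the safety analysis, says that "twelve patients will be enrolled onto each cohort and if the early stopping rule criterion are not met than approximately 12 additional patients" follow. Section 13.1.2 says that the cohorts "will be analyzed separately and initially enroll 12 patients to receive crenolanib with 1-2 courses of standard induction chemotherapy", with 12 more if the early criteria are not met. Neither mentions a check at 6.

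Sections 13.2.2 and 13.2.3 introduce the second check by reference to enrolment of the second 6. Section 15.2 schedules data safety meetings at least six-monthly or by number of patients enrolled (every 6 per cohort).

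**The concern.** A halting rule in a staged cohort protects the next group. The check at 6 exists for patients 7 to 12, and the check at 12 for patients 13 to 24. It can do that fully only if the count it uses is known before the next group is treated.

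Two things put that in doubt. First, a site working from the synopsis or Section 13.1.2 would see 12 patients as the first step and could enrol patients 7 to 12 with no check at 6. Second, even within Section 13.2 the wait is left to inference. The release is conditional on criteria defined to Day 60, but nothing says that earlier patients must have completed Day 60, and the timing statements that do exist follow enrolment rather than completed follow-up.

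Safety is a primary objective, and this phase decides whether a 72-patient expansion opens. The order of enrolling and checking should therefore not depend on which section is read.

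**Working it through.** **1. The plan's own boundaries.** Take each boundary as the smallest count r for which r/n exceeds the stated rate, with n = 6 and then cumulative n = 12. Section 13.2.1 gives the mortality limits: "enrollment in a cohort will be halted if the observed 30- and 60-day early mortality rate exceeds 10% and 20%, respectively". Sections 13.2.2 and 13.2.3 give 20% and 15%.

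| Rule | Rate to exceed | At 6 | At 12 | Agrees with text |
|---|---|---|---|---|
| Death by Day 30 | 10% | 1 (16.7%) | 2 (16.7%) | yes |
| Death by Day 60 | 20% | 2 (33.3%) | 3 (25.0%) | yes |
| Expected grade 4 by Day 60 | 20% | 2 (33.3%) | 3 (25.0%) | yes |
| Unexpected grade 4 by Day 60 | 15% | 1 (16.7%) | 2 (16.7%) | yes |

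All eight counts reproduce. The fault is in sequence and timing, not in the counts.

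**2. The staging, side by side.** Section 13.2 with its subsections gives 6 + 6 + 12 = 24. The synopsis and 13.1.2 give 12 + 12 = 24. The totals agree; the first step and the number of checks do not.

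**3. Timing at the fastest pace Section 13.2 allows.** Patients 1 to 3 start on study day 0 and patients 4 to 6 on day 30.

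| Patient 7 starts on | Situation | First 6 past Day 30 | First 6 past Day 60 |
|---|---|---|---|
| day 30 | no wait; spacing ends with patient 6 | 3 | 0 |
| day 60 | Day-30 count awaited, or spacing carried on | 6 | 3 |
| day 90 | Day-60 count awaited | 6 | 6 |

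The first group's Day-60 count is complete on day 30 + 60 = 90, so the gap is 30 to 60 days. If the toxicity clock runs from the first crenolanib dose (about Day 9, Section 5.8) rather than from the start of induction, the toxicity counts close about 8 days later.

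**4. How often a halt would come too late for patient 7.** Take the Day-60 mortality rule (2 or more of 6). Assume independent patients with true mortality p30 = 10% by Day 30 and p60 = 20% by Day 60, the plan's own limits.

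- Rule met in the end: 1 − 0.8^6 − 6 × 0.2 × 0.8^5 = 0.345.
- Chance of death in days 30 to 60 for a patient alive at Day 30: q = (0.20 − 0.10)/0.90 = 1/9.
- Patient 7 on day 30: enrolment is still open only if none of patients 1 to 3 has died, 0.9^3 = 0.729. The deaths to come are Bin(3, 1/9) + Bin(3, 0.2). P(0) = 0.360 and P(1) = 0.405, so P(2 or more) = 0.236. The product is 0.729 × 0.236 = 0.172.
- Patient 7 on day 60: enrolment is still open only if none of the six died by Day 30 (0.9^6 = 0.5314) and at most one of patients 1 to 3 died after it. P(2 or more of 6) − P(2 or more of the first 3), both at q = 1/9, is 0.1368 − 0.0343 = 0.1025. The product is 0.5314 × 0.1025 = 0.054.
- Patient 7 on day 90: 0.

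At the 7.9% and 19.7% that Section 13.2.1 cites from a relapsed/refractory trial, the same formulas give 0.337 for the rule being met, then 0.198 (day 30) and 0.078 (day 60). These results credit any halt already triggered by the Day-30 rule. The same sum cannot be done for the toxicity rules, because the documents give no onset times.

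**The case against.** The best defence is that Section 13.2 already contains the gate. It caps the first step at 6 and releases the next 6, and then the next 12, only if no stopping criterion is met. Criteria defined to Day 60 cannot be declared unmet earlier, so patient 7 must wait. On this view the 12 + 12 text is a summary into which 6 + 6 + 12 nests, and it defers to stopping criteria that are set out in 13.2. The meeting after every 6 patients in 15.2 supports steps of 6.

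Much of this stands. A reader might infer that the 30-day spacing is the only brake on enrolment. It is not: the cap of 6 and the conditional release are brakes too. The spacing also fits the Day-30 mortality rule and was not written as the gate to patient 7.

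A reader might also infer that the rules would protect nobody. The documents do not support that. The sponsor monitors adverse events continuously, serious events are notified within 24 hours, each enrolment needs sponsor confirmation, and a count reached early halts the cohort.

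The schedule in step 3 is also faster than the average pace. Spreading 120 patients over the stated 2 to 3 years gives 3.3 to 5 per month, or 1.7 to 2.5 per cohort if split evenly.

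What does not fall away is the clash between an initial 6 and an initial 12, and the missing statement of what follow-up releases the next group. Nesting does not settle either: neither 12 + 12 text says that patients 7 to 12 wait. Continuous monitoring cannot see events that have not yet happened.

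**Conclusion.** The point holds as an internal contradiction and an unstated wait. The first step is 6 in Section 13.2 and 12 in the synopsis and 13.1.2. Three of four rules count to Day 60, and no section ties release of patients 7 or 13 to completed Day-60 follow-up. This rests on the text alone.

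The protocol does not expressly permit patient 7 to start on day 30; that start is possible only if the conditional release is not read as a wait. The effect is partial leakage. With mortality at the plan's own limits, a Day-60 mortality halt that is still to come would be unseen when patient 7 starts with probability 0.172 (day 30) or 0.054 (day 60), out of 0.345 for the rule being met at all. Those figures assume the fastest permitted pace and independent patients; slower accrual would change them. The same gap in wording exists at the step from 12 to 24.

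Section 13.1 refers to a separate analysis plan. If that plan or a committee document already states the wait, the protocol needs only the alignment and a cross-reference.

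**What to change.** 1. Bring the synopsis safety analysis and Section 13.1.2 into line with the 6 + 6 + 12 staging of Section 13.2, naming both checks.
2. Add to Section 13.2 that patients 7 and 13 of a cohort are released only after the counts in 13.2.1 to 13.2.3 for all earlier patients in that cohort have been checked at the follow-up those rules define, and that any trigger reached sooner halts enrolment at once.
3. If the sponsor does not want to wait for full Day-60 follow-up, say so in 13.2 and state what follow-up the release decision uses.
4. Tie the second check in 13.2.2 and 13.2.3, and the safety-phase meetings in 15.2, to that follow-up rather than to enrolment. State whether Day 60 for toxicity runs from induction or from crenolanib.

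The cost is protocol wording plus a possible accrual pause of up to about two months at each of two steps per cohort. The cohorts enrol independently, so their pauses can overlap, and sponsor confirmation of each enrolment already gives the means to apply the rule.
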